6 ANALYSIS SETS

Membership of the analysis sets will be reviewed and agreed prior to DBL. These will be reviewed by the Sponsor, Study Statistician, PK analyst and Project Manager and signed off. If PK data is not available at the time of DBL, then subjects will be assumed to be included in the analysis set unless the PK data provide reason to exclude a subject, in which case this will be discussed with the Sponsor and documented within the Analysis Sets listing (Listing 16.2.3.1).

6.1 SAFETY SET

All randomised subjects who receive at least one dose of cytisine will constitute the Safety Set.

This analysis set will be used for baseline and safety summaries as well as for all study listings.

6.2 PK SET

The PK Set will include all subjects who have completed all cytisine dosing on Days 1-3, completed >90% cytisine dosing on Days 4-25 and comply with the following criteria:

- Do not have an occurrence of vomiting or severe diarrhoea which renders the concentration profile unreliable (i.e. vomiting occurring at or before 2 times median T_{max});
- Do not use a concomitant medication which renders the concentration profile unreliable;
- Have at least one evaluable concentration that is preceded by a lower evaluable concentration and followed by a lower evaluable concentration for the calculation of C_{max} , T_{max} and AUCs (i.e. at least 3 evaluable concentrations in total);
- Do not violate the protocol (major protocol deviation) in a way that may invalidate or bias the PK results.

6.3 PD SET

The PD Set will include all subjects in the PK Set who have an available baseline result and at least one on-treatment result with regards to urine cotinine, expired air CO or daily cigarette consumption and do not incur a major protocol deviation in a way that may invalidate or bias the PD results.

6.4 ECG SET

The ECG Set will include all subjects who receive at least one dose of cytisine, with at least one available baseline ECG and at least one on-treatment ECG.

6.5 ECG-PK SET

The ECG-PK Set will include all subjects who receive at least one dose of cytisine, with a time-matched ECG-PK pair at baseline and at least one time-matched pair on-treatment.

7 SAFETY MONITORING

Not applicable.

8 INTERIM ANALYSES

Not applicable.

9 DATA

9.1 CRF DATA

CRF data will be provided by [REDACTED] Data Management to the Statistics department as SAS datasets in [REDACTED] standard format. SDTM datasets will be derived from the raw database and ADaM from SDTM. Both SDTM and ADaM domains will be used for programming the outputs to be included in the Clinical Study Report (CSR). SDTM/ADaM programming will begin when populated [REDACTED] standard SAS datasets are available.

9.1.1 Laboratory Data

Transfers of safety laboratory data will be available from the Pathology laboratory and delivered to Data Management via electronic transfer and stored within the study database. Details of laboratory data are documented in the Data Management Plan (DMP). Populated test transfers will be received before programming can start. The following results will be included:

- **Haematology:** Haemoglobin, haematocrit, mean cell volume, mean cell haemoglobin, mean cell haemoglobin concentration, red blood cells, white blood cells, neutrophils, lymphocytes, monocytes, eosinophils, basophils and platelets.

- **Biochemistry:** Total protein, albumin, total bilirubin, alanine transaminase, aspartate transaminase, gamma glutamyl transferase, alkaline phosphatase, glucose, sodium, potassium, calcium, bicarbonate, creatinine and urea.
- **Urinalysis:** Glucose, specific gravity, protein, leukocytes, ketones, urobilinogen, bilirubin, nitrites, pH and blood.
- **Microscopy:** In the event that the 'dipstick' is positive for leukocytes, nitrites, protein and blood, the parameters red blood cells, white blood cells, epithelial cells, crystals, bacteria and casts will be examined microscopically.
- **Virology:** Hep B, Hep C and HIV.
- **Drugs of Abuse and Alcohol:** Urine alcohol and drugs of abuse screen: cannabinoids, amphetamines, cocaine, benzodiazepines, opiates and cotinine.
- **Urine cotinine:** Urine cotinine will be collected throughout the study as a PD parameter.
- **Pregnancy/post-menopausal assessment:** serum/urine pregnancy test and follicle stimulating hormone.
- **Other parameters:** Any further parameters that are taken that are not included as part of the above categories will be included in an 'Other Laboratory Data' listing.

9.1.2 Pharmacokinetic Data

Plasma and urine concentration data will be received as an Excel file from the Bioanalytical department via an electronic transfer and stored as a SAS dataset. This data will then be stored in the appropriate SDTM domain and subsequent ADaM domain which will be used to produce the file provided to the pharmacokinetic team in order to derive the PK parameters using Phoenix WinNonlin 6.4. Derived PK parameters will be received by the Statistics department from the Project Manager/PK analyst in a SAS.xpt file in an agreed format and then stored as a SAS dataset and subsequently within SDTM/ADaM domains.

9.1.3 ECG Holter Monitoring Data

ECG Holter data will be received as an Excel file from CardioAnalytics (3rd party cardiac monitoring service managed by ████████) via an electronic transfer and stored as a SAS dataset. This data will then be stored in the appropriate SDTM domain and subsequent ADaM domain.

9.2 RANDOMISATION LIST

The randomisation list will be uploaded to a SAS dataset and incorporated into the relevant SDTM/ADaM domains.

9.3 PROGRAMMING AND DATA REVIEW

Programming of datasets, tables, figures and listings may be ongoing while study data management activities are in progress.

Prior to DBL, a review of the clinical database (i.e. CRF data, laboratory data) in the form of Excel data listings will be conducted. A Data Review Meeting (DRM) will be held to discuss the outcome of this review, any potential impact on the analyses, analysis sets and protocol deviations. Once all data issues have been resolved and the analysis sets approved, the database will be locked. The SDTM/ADaM datasets will be finalised and the final run of outputs and quality control (QC) will take place.

Due to issues with the recruitment of the elderly cohort, two database locks are required. The database for non-elderly subjects (≤ 65 yrs) will be locked while recruitment for the elderly cohort (> 65 yrs) is ongoing. The database for the elderly subjects will be locked at a later date. Therefore, two sets of TFLs will be produced – an ‘interim’ set presenting data for the non-elderly subjects only followed by a second set which will include data from both the non-elderly and elderly cohorts. The second set consisting of data from all subjects will be included in the clinical study report (CSR).

10 STATISTICAL METHODS

10.1 GENERAL PRINCIPLES

- All statistical methods will be based on the International Conference on Harmonisation (ICH) E9 document “Statistical Principles for Clinical Trials”.
- All data collected will be presented within data listings and any unscheduled visits will be listed.
- Data will be summarised by dose group (1.5 mg Cytisine, 3.0 mg Cytisine), age group (18-65 yrs, > 65 yrs, all ages) and overall (both dose groups pooled) where appropriate. The format of the summaries is defined in the shells at the end of this document.
- In summary and analysis tables of continuous variables, standard descriptive statistics (N [number within analysis set, or cohort, or subgroup], n [number of observations included in analysis], mean, standard deviation [SD], median, minimum and maximum) will be presented. Least squares mean (LS mean) and 90/95% confidence interval (CI) will be presented in the statistical analysis outputs as appropriate. For PK summaries, geometric mean, and coefficient of variation (%CV) will also be used to summarise the data.
- Unless otherwise specified, the minimum and maximum statistics will be presented in summary tables to the same number of decimal places as the original data. The mean, median, LS mean, geometric mean and CI will be presented to one more decimal place than the original data. SD will be presented to two more decimal places than the original data. %CV will be presented to one decimal place.
- In summary tables of categorical variables, the number of non-missing observations by category will be presented along with percentages. Unless otherwise specified, the denominator for each percentage will be the number of non-missing observations. All percentages will be presented to one decimal place.
- All plots will use a linear time scale for the nominal times of the visits and will be labelled by time point.
- Original values will be used in summary tables, unscheduled measurements will be listed only. However, where repeats of baseline values occur, unless specified otherwise (i.e. 12-lead ECG), the last assessment will be used within any summary tables and used to calculate change from baseline. In case an unscheduled measurement is performed immediately after the scheduled

measurement due to an error in the original measurement, unless specified otherwise (i.e. 12-lead ECG) the unscheduled measurement will be included in the analysis and the original erroneous measurement will be excluded.

- The date format for all output presentations will be as captured in the database.
- All statistical analysis will be performed using SAS 9.3 or higher.
- All hypothesis testing will be carried out at the 5% (2-sided) significance level unless stated otherwise.
- P-values will be rounded to four decimal places. P-values less than 0.0001 will be reported as <0.0001 in tables.
- Generally, character values will be left aligned and numeric values will be decimally aligned.
- If any of the assumptions underlying the formal statistical methods proposed are violated during the analysis of the final data, alternative statistical methods will be used and any changes documented in the statistical methods section of the clinical study report (CSR), including the rationale for use.
- For numeric data which includes non-numeric values (e.g. PK data reported as BLQ or laboratory results reported as < 10 or >100) the following principles will be applied when summarising the data:
 - BLQ will be replaced with a zero.
 - Results reported as <x or >x will be treated as x.

10.2 STRATIFICATION AND COVARIATE ADJUSTMENT

In order to investigate any possible effects of age, analyses will be presented by non-elderly subjects (18-65 years) and elderly subjects (>65 years).

10.3 MISSING DATA

Generally, no methods to impute missing data will be used. However, for the purpose of calculating change from baseline, in the instance of a missing baseline result (generally the assessment at Day 1, Pre-Dose) the results obtained at the Screening/Day -1 visit will be used instead, if available.

In the instance of missing pharmacokinetic blood samples, the linear-up/log-down trapezoidal rule will be employed between the samples immediately before and after the missing sample for the AUC calculations.

10.4 POOLING OF SITES

Not applicable.

10.5 MULTIPLE COMPARISONS

Not applicable.

10.7 STATISTICAL ISSUES

None.

11 STATISTICAL OUTPUT

General principles for layout of the statistical output are described in Section 10.1. Layout and specifications are illustrated for each unique table and listing within the shells presented in Section 14.

11.1 SUBJECT DISPOSITION

The subject disposition table will summarise the following data for all randomised subjects:

- The number (%) of subjects within each analysis set;
- The number (%) of subjects dosed;
- The number (%) of subjects who completed the study/withdrew from the study and the associated reasons for early study termination.

The disposition summary will be presented by dose group and overall.

Screening and study completion/termination data will also be listed. A listing of all subjects with protocol deviations will be presented including major/minor classification. A data listing presenting subject eligibility for each analysis set and the reason for exclusion from an analysis set will also be presented.

11.2 SUBJECT CHARACTERISTICS AT BASELINE

11.2.1 Demographic and Baseline Characteristics

Demographic data will be listed (including informed consent information) and descriptive statistics for the continuous variables age, height, weight and BMI and frequencies for the categorical variables race and gender will be tabulated. These descriptive statistics will be presented by dose group, age group and overall.

Alcohol and cotinine results collected at Screening and Day -1 will be listed and summarised using frequencies (n, %).

Demographic and baseline data will be listed and summarised using the Safety Set. Demographic data may also be summarised using the PK Set, if appropriate.

Smoking history variables reported at baseline will be listed and summarized by dose group, age group and overall. The total number of cigarettes smoked in the past 24h will be summarized as a continuous

variable, and also using frequencies (n, %). Descriptive statistics will be reported for baseline expired CO (ppm), urine cotinine, FTND total score, and TCQ-SF total score. Baseline is defined as results obtained at Screening for expired CO and urine cotinine and as Day -1 for the daily cigarette consumption, FTND and TCQ-SF.

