**Figure 4: Dose Timing and Total Daily Dose**

Days	Regimen	Total Daily Dose		Approximate Interval
		1.5 mg Dose	3.0 mg Dose	
1-3	6 times daily	9.0 mg	18.0 mg	2 hours
4-12	5 times daily	7.5 mg	15.0 mg	2.5 hours
13-16	4 times daily	6.0 mg	12.0 mg	3 hours
17-20	3 times daily	4.5 mg	9.0 mg	4-5 hours
21-24	2 times daily	3.0 mg	6.0 mg	6 hours
25	Once daily	1.5 mg	3.0 mg	-

A total of 9 overnight stays in the clinic will be required over the 26-day study period. Subject entry into the study may be staggered in groups in order to facilitate study management activities but all subjects passing screening are to provide clinic visits as follows:

- Day -1 and Days 1-3 (4 overnight stays in clinic): Arrive at study clinic in the afternoon of Day -1, repeat select screening testing and verification of inclusion/exclusion criteria. Provide risks of smoking and quit advice according to WHO guidelines that evening. All subjects will fast for minimum of 10 hours prior to first dose on Day 1. Randomisation to treatment Group assignment will occur on the morning of Day 1, just prior to starting treatment. On the morning of Day 1, obtain baseline blood and urine and CO level, initiate Holter monitoring, receive study drug packets, begin treatment and provide required blood and urine samples. Subjects may have breakfast after first dose and continue with a standard meal schedule. On Days 1-3, various safety assessments and blood sample collections will occur. On the morning of Day 4 complete vital signs, ECG, blood for haematology and biochemistry testing, urine for cotinine test, expired CO, completion of tobacco craving questionnaire, safety assessment and collection of the pre-dose PK blood draw. Subject will then take first Day 4 dose followed by risks of smoking and quit advice, review of diary requirements, reminder of next clinic visit date and will be discharged.
- Day 4-11: Subjects to maintain dosing as per schedule.

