### **6.1. Inclusion Criteria**

#### **6.1.1. To be Confirmed at Screening**

1. Regular moderate cigarette smokers (minimum 10 cigarettes per day) who want to stop smoking.

2. Urine cotinine >500 ng/mL.
3. Expired air carbon monoxide (CO) > 11 parts per million (no cigarette 1 hour before test).
4. Healthy males and females 18-65+ years of age.
  - a. If a female subject of child bearing potential, a negative pregnancy test at screening and admission and willing to use an effective method of contraception (unless of non-childbearing potential or where abstaining from sexual intercourse is in line with the preferred and usual lifestyle of the subject) from first dose until 3 months after last dose of cytisine.
  - b. If a female subject of non-child bearing potential, a negative pregnancy test at screening and admission. For the purposes of this study, this is defined as the subject being amenorrheic for at least 12 consecutive months or at least 4 months post-surgical sterilisation (including bilateral fallopian tube ligation or bilateral oophorectomy with or without hysterectomy). Menopausal status will be confirmed by demonstrating at screening that levels of follicle stimulating hormone (FSH) fall within the respective pathology reference range. In the event a subject's menopause status has been clearly established (for example, the subject indicates she has been amenorrheic for 10 years), but FSH levels are not consistent with a post-menopausal condition, determination of subject eligibility will be at Investigator's discretion following consultation with the Sponsor.
  - c. If a male subject, willing to use an effective method of contraception (unless anatomically sterile or where abstaining from sexual intercourse is in line with the preferred and usual lifestyle of the subject) from first dose until 3 months after last dose of cytisine.
5. Subject with no clinically significant abnormal serum biochemistry, haematology and urine examination values within 28 days before the first dose of cytisine.
6. Subject with negative urinary drugs of abuse screen, determined within 28 days before the first dose of cytisine (a positive alcohol result may be repeated at Investigator's discretion).
7. Subject with negative human immunodeficiency virus (HIV), hepatitis B surface antigen (Hep B) and hepatitis C virus antibody (Hep C) results.

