## **7.2. Smoking, Diet and Fluid Restrictions**

### **7.2.1. Smoking**

There will be minimal restrictions to smoking during days of confinement, such as all smoking must occur within designated area(s) only and subjects cannot smoke during active PK sampling period (i.e. subjects must have their last cigarette a minimum of 2 hours before dosing and can only start smoking after final PK sample). Subjects will go for a cigarette as a group and will need to have their last cigarette before 23:00 while they stay in the clinic. Clinic staff will review these guidelines with subjects during confinement and will monitor compliance.

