### **8.8. Selection and Timing of Dose for Each Subject**

First dose will be administered at approximately 9.00 a.m. on Day 1. Additional doses will be as per the Dosing Schedule (see [Figure 4](#)). A target time will be provided for each dose in the diary and actual time of dose will be recorded. For Days where dosing is every 2 to 3 hours, dosing should be  $\pm$  10 min within the targeted time. For Days where dosing is every 4-6 hours, dosing should be  $\pm$  30 min within the targeted time.

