 Vital signs (supine blood pressure, pulse rate and oral temperature) will be recorded at pre-dose and again prior to discharge from clinic. Vital signs will also be recorded 3 hours post last dose on Days 1, 2, 3, 12, 16, 20 and 24.

 Clinically relevant changes will be reported as adverse events.

 Obtain 12-lead ECG (triplicate) at any time if clinically indicated during clinic visits. Repeat 12-lead ECG and assess prior to discharge.

 Attach ECG Holter monitor and begin recording prior to first dose on Day 1 and continue for 24 hours (discontinue just prior to first dose on Day 2. Repeat again by starting Holter monitor prior to dose on Day 25 and record for 24 hours.

 Haematology and biochemistry testing to be completed prior to discharge on Days 4, 13, 17, 21, 26

 Urine cotinine and expired CO testing to be obtained at screen and prior to discharge on Days 4, 13, 17, 21, 26.

 Each subject given advice about the risks of smoking and quitting. This will take the form of a brief interview following WHO evidence-based recommendations on the treatment of tobacco dependence on Day -1 and reminders prior to discharge on Days 4, 13, 17, 21, 26 and on the final post-study visit.

 IMP administration to follow 25-day dosing schedule (see Figure 4).

 Plasma collection for PK analysis is outlined in Section 12.1.

 Urine to be collected for PK on Day 1 and Day 25 as follows: pre-dose and 0-24 hours.

 Adverse event recording to begin upon admissions on Day -1 to post study.

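### Protocol 5.1 names a Day 1 baseline CO that the schedules and SAP omit; change from Screening CO probably overstates the within-group fall

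*SAP*

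**What the plan says.** Protocol 5.1, in the visit outline under Figure 4, has subjects "Arrive at study clinic in the afternoon of Day -1" and then: "On the morning of Day 1, obtain baseline blood and urine and CO level, initiate Holter monitoring".

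Footnote 11 to Table 6 gives a different list: "Urine cotinine and expired CO testing to be obtained at screen and prior to discharge on Days 4, 13, 17, 21, 26". The footnote to the SAP 3.4 schedule is the same. The Day 1 procedure list in Protocol 11.2.3 contains no CO test.

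SAP 11.2.1 says "Baseline is defined as results obtained at Screening for expired CO and urine cotinine", and SAP 11.5.1 tabulates CO change from Screening. SAP 1.2, which lists departures from the protocol, does not mention this.

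The Screening reading is an entry criterion (Protocol 6.1.1): "Expired air carbon monoxide (CO) > 11 parts per million (no cigarette 1 hour before test". In the clinic, Protocol 7.2.1 says "There will be minimal restrictions to smoking during days of confinement", but subjects "will need to have their last cigarette before 23:00 while they stay in the clinic". Around PK sampling they may not smoke from 2 h before dosing until the final sample.

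**The concern.** Reduction in expired CO from baseline is one of six PD endpoints under the primary variables in SAP 4.1. There is no untreated arm, so the within-group change is what a reader would take as evidence of reduced smoking.

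The two ends of that change are measured under different conditions. At Screening, up to 28 days before dosing, a subject may have smoked an hour earlier and must read above 11 ppm. On Days 4, 13, 17, 21 and 26 the test follows a night in the clinic under the smoking limits. If the smoke-free interval is longer on treatment, CO falls even in someone whose smoking has not changed. Selecting on the Screening value pushes the same way.

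The plan also leaves a choice open. If the site did record a Day 1 CO under Protocol 5.1, the general rule in SAP 5 (last value before first dose) would select it, while SAP 11.2.1 and 11.5.1 select Screening.

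**Working it through.** The documents give no CO variance, half-life or bias figure, so there is nothing to reproduce. What follows is illustrative.

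**Inputs from the documents.** Screening: at least 1 h smoke-free, CO above 11 ppm (Protocol 6.1.1). Non-smoker level: 0–6 ppm (13.4.2). Overnight cut-off: 23:00 (7.2.1). First dose near 09:00, stated for Day 1 only (8.8: "First dose will be administered at approximately 9.00 a.m. on Day 1").

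**Assumptions.** Screening CO S = 20 ppm (12–30); background b = 3 ppm (0–6); half-life HL = 4.5 h (2–8); smoke-free hours at Screening g = 1 to 4.

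**Smoke-free time.** For an unchanged smoker tested h hours after the last cigarette:

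CO(h) = b + (S − b) × 0.5^((h − g)/HL)

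| h | g = 1 | g = 2 | g = 4 | Range over all assumptions |
|---|---|---|---|---|
| 10 h (23:00 to 09:00) | 7.25 ppm (−64%) | 7.96 (−60%) | 9.75 (−51%) | −20% to −96% |
| 2 h (morning cigarette) | 17.57 (−12%) | 20.0 (0%) | 26.13 (+31%) | g = 1: −4% to −29%; g = 4: +9.5% to +100% |

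Example, h = 10 and g = 1: 3 + 17 × 0.5^(9/4.5) = 3 + 17 × 0.25 = 7.25.

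**Selection on the entry reading.** With no true change, the expected fall is (1 − ρ) × SD × φ(a)/(1 − Φ(a)), where a = (11 − μ)/SD. For assumed μ = 16, SD = 8, ρ = 0.7 this is 1.1 ppm (5.5% of the Screening mean). Over μ 12–25, SD 6–10, ρ 0.5–0.9 it runs from 0.02 to 3.7 ppm (0.1% to 19%). It is always a fall, and usually much smaller than the 10 h effect.

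**How well Day 1 matches later visits.** No PK sampling falls on the evening of Day -1, so smoking is possible until 23:00: 10 h before a 09:00 test. For later visits, take a 09:00 first dose, the Figure 4 intervals and a literal reading of 7.2.1:

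- Day 3: sixth dose at 09:00 + 5 × 2 h = 19:00; sampling ends 5 h later, at 24:00, past the cut-off. Last cigarette by 17:00, so 16 h before a 09:00 test on Day 4.
- Day 12: fifth dose at 09:00 + 4 × 2.5 h = 19:00; sampling ends at 23:00. Again 16 h, before Day 13.
- Day 16: fourth dose at 18:00; sampling ends at 22:00. Smoking is possible until 23:00, so 10 h before Day 17.
- Day 20: third dose at 17:00 (4 h intervals) or 19:00 (5 h); 10 h or 16 h before Day 21.
- Day 25: smoke-free from 2 h before the dose to the 24 h sample, so 26 h before Day 26.

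At 16 h with g = 1, CO = 3 + 17 × 0.5^(15/4.5) = 4.69 ppm. From Screening the fall is (20 − 4.69)/20 = 77%. From a 10 h Day 1 value it is (7.25 − 4.69)/7.25 = 35% (4–88% over the ranges).

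**Room to fall.** From a 10 h Day 1 baseline a full quitter can drop 7.25 − 3 = 4.25 ppm (g = 1) to 9.75 − 3 = 6.75 ppm (g = 4), against 20 − 3 = 17 ppm from Screening: 25–40% of the room (range 4–59%).

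**The case against.** **The SAP is consistent with itself.** A reader might infer that it breaks its own baseline rule. It does not: SAP 5 allows Screening when a Day 1 assessment is not planned, and the schedules plan none. The conflict is between Protocol 5.1 and everything downstream. This stands.

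**The sign is not settled.** Protocol 7.2.1 calls the clinic limits minimal and does not rule out a morning cigarette before the later tests. With one, the illustration gives anything from a small fall to a rise. This also stands, and is why the claim is only that an overstated fall is probable.

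**Day 1 is not the same kind of night.** Correct, as the timing above shows. But the longer interval before later visits worsens the Screening comparison more (77% against 35%).

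**Day 1 could do worse.** If Day 1 is read at 10 h and a later visit at 2 h, an unchanged smoker shows a false rise of 17.57 − 7.25 = 10.3 ppm (g = 1) to 26.13 − 9.75 = 16.4 ppm (g = 4), against −2.4 to +6.1 ppm from Screening. That supposes a morning cigarette on later days but not on Day 1, although 7.2.1 sets the same morning rules for both. It is a reason to record time since last cigarette and to keep both baselines.

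**Little is at stake.** Absolute CO by visit is already tabulated and plotted (SAP 11.5.1). Cessation at Day 26 uses absolute CO below 10 ppm and needs no baseline. No hypothesis test is planned (SAP 3.5). This limits the weight of the point but does not remove it.

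**Conclusion.** The mismatch is plain in the text. Change from Screening CO probably overstates the within-group fall, because the smoke-free interval is likely to be longer on treatment and because Screening is the entry reading. The size cannot be derived from the documents. The 51–64% figure rests on an assumed Screening level, background and half-life and on 10 smoke-free hours; a cigarette shortly before the test can cancel or reverse it.

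Three stronger readings are not supported:

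- The dose comparison is not shown to be biased. Randomised groups follow the same rules, so the 1.5 mg versus 3.0 mg contrast, which SAP 10.6 names as primary, is largely unaffected.
- A certain 26 h abstinence before Day 26 needs a literal reading of Protocol 7.2.1, while the Day 25 list still records cigarettes smoked.
- Day 1 is not shown to be good enough to replace Screening outright, given the floor effect and the partial match.

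This is a worthwhile, inexpensive improvement to a descriptive primary PD endpoint, not a flaw that invalidates the analysis.

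**What to change.** - Reconcile Protocol 5.1 with Table 6 footnote 11, the Day 1 list in 11.2.3, the SAP 3.4 schedule and SAP 11.2.1/11.5.1 by listing the Day 1 pre-dose CO. First check whether the site already recorded one.
- Report change from Day 1 pre-dose CO alongside change from Screening wherever a Day 1 value exists.
- Record time since last cigarette at every CO test, including Screening and Day 1, and show it beside the results.
- State that change from Screening is not by itself to be read as a drug effect. Where no Day 1 value exists, rely on the absolute CO by visit already planned.

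No change to the cotinine baseline is proposed.

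The cost is one breath test on a morning when subjects are already in the clinic, one CRF field per CO test, and SAP wording. Three downsides should be stated in the SAP. Day 1 only partly matches later visits: there is no PK sampling on the evening of Day -1, but there is before Days 4, 13, 17 and 21, and a literal reading of Protocol 7.2.1 makes the interval before Day 26 longer still. It leaves less room for CO to fall. And because SAP 9.3 locks the non-elderly data while elderly recruitment continues, subjects already dosed may have Screening only; a new test might then reach mainly the elderly (12 of 36 planned), and Screening stays the common baseline across age cohorts.
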